5.5. Derivation and Transformation on Data

5.5.1. Baseline Values

Two baselines (Main Study and OLE baselines) are defined as below. Both baselines can be used to analyze data collected during OLE period. Only Main Study Baseline will be used to analyze data collected during Main Study portion.

5.5.1.1. Main Study Baseline

The Main Study Baseline value for efficacy and safety is the last non-missing observed data prior to the first dose of study drug. Since per SoA all Baseline Visit (V2) assessments (except

post-dose ECGs at V2) are performed and recorded prior to participants taking their first dose of study drug, the baseline value will include observations on or prior to the date of first dose of study drug. For ECGs, the Baseline value is the average of the 3 (triplicates) ECGs performed at Baseline before first drug administration.

5.5.1.2. OLE Baseline

OLE Baseline is defined as the last non-missing observed data prior to the first dose of pridopidine in the OLE period. In general, the OLE Baseline will be the OLE Day 1 assessment. For ECGs, the OLE Baseline value is the average of the 3 (triplicates) ECGs performed at OLE Day 1 visit before first drug administration.

Change from Baseline analysis of ECGs will be performed using Main Study or OLE Baseline as appropriate.

5.5.2. Baseline Age

Due to data protection requirements only year of birth and age at time of signing consent will be captured on the eCRF and no computation of age will be necessary.

5.5.3. Study Day and By-Visit Summaries

If the date of interest (date of visit, date of start of medication, date of AE, etc.) occurs on or after the first dose date then study day will be calculated as (date of interest – date of first dose) + 1. If the date of interest occurs prior to the first dose date, then study day will be calculated as (date of interest – date of first dose). Study Day 1 is the date of first dose and as per CDISC Study Data Tabulation Model Implementation Guide (SDTMIG) 3.2 requirements, there is no Study Day 0.

For by-visit summaries and/or statistical models for efficacy, ET visit for a specific measure will be assigned to the next closest non-missing planned scheduled visit of this measure.

5.5.4. Change and Percent (%) Change from Baseline

Observed change in values from Baseline (i.e., Day 1) is calculated as (post-Baseline result – Baseline result).

Observed % change in values from Baseline is calculated as $[100 * (\text{post-Baseline result} - \text{Baseline result}) / (\text{absolute value at Baseline result})]$.

If either the Baseline or the post-baseline result is missing, the observed change from Baseline is set to missing as well. If the Baseline result is missing or 0, or if the post-baseline result is missing, then observed % Change from Baseline will be set to missing at that visit.

For UHDRS -TFC and other efficacy assessments, change from Baseline will be calculated for scheduled in-clinic visits at Weeks 26, 39, 52, 65, and 78. For other efficacy and safety endpoints, change or % change (where applicable) from baseline to post-baseline visits will be calculated per SoA.

5.5.5. End of Study Definition

End of the Main Study occurs when the last participant has completed the Week 65 visit or has withdrawn from the study. At End of the Main Study, a participant should have either completed the double-blind period between Week 65 and Week 78 or discontinued early from the study.

End of OLE is defined as having occurred when the last participant completes the OLE period of the study or has withdrawn from the study during OLE period.

5.5.6. Last Study Drug Date for the Main Study Analyses

For participants that continue beyond Week 65, the last study drug date for the Main Study analyses will be derived from the last date of study drug administration on the eCRF page, End of Treatment, in the Main Study.

5.5.7. Study Periods

End of Study Day for each participant

End of the Main Study Day (double-blind period) for a participant is defined as the Main Study EoS/ET Visit, or last follow-up safety visit or phone call in the Main Study. **End of OLE Day** for a given participant is defined as the last follow-up safety visit or phone call for final data collection in the OLE period.

A participant is considered as a **Week 65 Completer (Main Study Completer)** if he/she has completed the Week 65 Visit without discontinuing earlier, regardless of whether they were on or off study treatment at Week 65. As per the study design, these participants may have completed visits beyond Week 65.

Treatment periods

Main Study Treatment Period is defined as the period from the first dose to the End of the Main Study Day. **OLE Treatment Period** is defined as the period from 1 day after End of the Main Study Day to End of OLE Day.

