As soon as the last participant reaches Week 65, the Main Study End of Study (EoS) visit for all remaining participants who are between Week 65 and Week 78 needs to be conducted within 4 weeks.

For participants who complete their Week 65 visit within 4 weeks of the last participant completing Week 65, the Week 65 visit will be considered the EoS Visit. For participants who are beyond 4 weeks from their Week 65 visit when the last participant reaches Week 65, and have not had a Week 78 visit, the EoS visit will be conducted within 4 weeks.

The double-blind will be maintained for all participants and Investigators. Following database lock at the end of Main Study, the treatment assignment will be unblinded for analysis. Details of

personnel unblinded and for those who the blind will be maintained are outlined in the Blinding-Unblinding Plan.

[figure not shown]
For each participant, the last visit in double-blind treatment period will be the Main Study EoS visit scheduled between Week 65 and Week 78 if the participant completes all study visits, or Early Termination (ET) visit if the participant withdraws from the study before Week 65.

At the Main Study End of Study (EoS) visit, eligible participants will have the option to enroll into an OLE period, commencing at the Main Study EoS visit and consisting of a 2-week up-titration period and a maintenance period, and to receive pridopidine until 12 months after the last participant completes the double-blind treatment period. The OLE duration may be extended pending emerging data from the double-blind portion of the study. The Sponsor intends to submit a substantial protocol amendment for the extension of the OLE after ensuring that the benefit-risk ratio remains positive following analysis of the data from the Main Study.

Participants, who are not continuing to the OLE study, will be contacted by phone for a safety evaluation of 2 weeks after the Main Study EoS/ET visit. AEs will be monitored for these 2 weeks until the safety telephone contact.

[figure not shown]
Throughout the study, participants will be assessed through on-site clinic visits, virtual visits (VV) (by phone which may be via regular telephone, smart phone, tablet or computer), as specified in the corresponding schedule of activities (SoA) ([Table 1](#) – Main Study, and [Table 2](#) – OLE) and study schema ([Figure 1](#) – Main Study, and [Figure 2](#) – OLE).

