- b. This period is variable in duration up to 13 weeks. Participants will continue to receive treatment during the double-blind variable period until they reach Week 78 or until the last participant randomized completes 65 weeks of treatment (2 weeks titration + 63 weeks full-dose), whichever comes first. As soon as the last participant reaches Week 65, the Main Study EoS visit for all remaining participants who are 4 weeks beyond their respective Week 65 visit needs to be conducted within 4 weeks.
- c. Follow-up visit in Main Study is only applicable to participants who are not continuing to Open-label Extension.
- d. All Baseline assessments should be done pre-dose, except post-dose ECG.
- e. For the last group of participants whose Week 65 visit is within 4 weeks of last participant's Week 65 visit in the Main Study, the End of Study visit will be V7.
- f. After completing the Main Study EoS visit, eligible participants will have the option to continue for an Open-label Extension.
- g. When a participant discontinues study drug but continues to be followed in the study, they should first do ET visit and then continue with the follow-up off study treatment as scheduled.
- h. Visit window can be expanded any post Week 4 (V3) in-clinic visit window to ±28 days; this applies to V4-8. The expansion of the in-clinic visit window is only in case of a global pandemic.
- i. To be done once, as early as Main Study Week 58, or at V7 (Main Study Week 65)/Main Study Week 72 (depending on when the participant is anticipated to transition to OLE).

- j. Inclusion/exclusion criteria should be met before Baseline visit.
- k. Safety laboratories should not be collected for participants who are off drug and remain in the study, unless there are abnormalities requiring follow-up.
- l. Serum pregnancy test will be performed at Screening. At Baseline visit, urine pregnancy test will be performed before first dose. Both test results must be known before first dosing. Urine pregnancy test will be performed at subsequent timepoints. An indeterminate or positive reading for the urine pregnancy test should be followed-up by a serum pregnancy test and the participant should be referred to a gynecologist if required. During the Treatment period, urine pregnancy test will be performed monthly. Refer to Protocol Appendix 4 Section 10.4.
- m. Single ECG to assess eligibility.
- n. Baseline pre-dose assessment will include triplicate ECG administrations.

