- o. Single ECG 1-2 hours post-dose.
- p. Single ECG pre-dose.
- q. Only for participants not continuing to Open-label Extension (single ECG). Participants continuing to OLE, will have triplicate ECG (pre-dose) at V8.
- r. Vital signs (body temperature, systolic and diastolic blood pressure, and heart rate) will be measured in a supine position after 5 minutes rest; thereafter, blood pressure should be measured again after standing for 2 minutes.
- s. For training purposes only.
- t. This information will be collected as part of the concomitant medication inquiry.
- u. Blood samples for plasma concentration of study drug will be collected 1-2 hours after dosing and after the ECG. PK samples should not be collected from participants who are off drug and remain in the study.
- v. Always collect blood after ECG is administered (not before).
- w. Sample analysis will be drawn at Screening or Baseline.
- x. Sampling analyses for deoxyribonucleic acid (DNA) extraction will be performed only once during the study, at Screening or at Baseline, for future genetic analysis related to pridopidine response or HD.
- y. Sampling analyses for CAG, only if needed.

Table 2: Schedule of Activities – Open-label Extension

Study Period Procedures and assessments	Open-Label Titration Period		Open-Label Full-dose Treatment Period					Follow-up Safety Assessment	
	Study Clinic Visit	OLE V1 ^a (same as Main Study V8)	OLE V2	OLE V3	OLE V4+	OLE EoS/ET ^b	OLE F/U		
Telephone Call Safety Visit		📞	📞	📞					📞
OLE Study Week	OLE Day 1 (same as Main Study Wk 78/EoS)	OLE Wk 2	OLE Wk 4	OLE Wk 13	OLE Wk 26	OLE Wk 39 & every 26 wks thereafter	OLE Wk 52 & every 26 wks thereafter	X	+2 weeks after OLE EoS/ET
Visit Windows (days)		±1	±5	±5	±14	±14	±14	±14	±5
OLE Informed consent	X (if not obtained at Main Study V7)								
Re-confirm eligibility to OLE	X								
Clinical laboratory tests (serum chemistry, hematology) ^d	X		X		X		X	X	
Urinalysis ^e	X								
Pregnancy test (for WOCBP)	U		U		U		U	U	
Monthly urine pregnancy test (at home)									
Brief physical examination	X (full PE)		X		X		X	X	
12 lead ECG	X ^{f,g}		X ^g		X ^h			X ^h	
Vital signs	X		X		X		X	X	
C-SSRS (since last visit version)	X		X	X	X	X	X	X	X
UHDRS-TFC	X				X		X	X	
UHDRS-TMS	X				X		X	X	
SDMT	X				X		X	X	
SWR	X				X		X	X	
Q-Motor	X		X		X		X	X	
PBA-s (Short Form)	X		X		X	X	X	X	X
CGI-C	X				X		X	X	
HDQoL	X				X		X	X	

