Study Period Procedures and assessments	Open-Label Titration Period		Open-Label Full-dose Treatment Period					Follow-up Safety Assessment	
	OLE V1 ^a (same as Main Study V8)		OLE V2		OLE V3		OLE V4+	OLE EoS /ET ^b	OLE F/U
Study Clinic Visit									
Telephone Call Safety Visit		📞		📞		📞			📞
OLE Study Week	OLE Day 1 (same as Main Study Wk 78/EoS)	OLE Wk 2	OLE Wk 4	OLE Wk 13	OLE Wk 26	OLE Wk 39 & every 26 wks thereafter	OLE Wk 52 & every 26 wks thereafter	X	+2 weeks after OLE EoS/ET
Visit Windows (days)		±1	±5	±5	±14	±14	±14	±14	±5
Benzodiazepines and antidepressants inquiry	X	X	X	X	X	X	X	X	X
Alcohol/illicit drug use inquiry	X	X	X	X	X	X	X	X	X
Dispense/collect study drug	X		X		X		X	X (collect only)	
Review study compliance and adherence	X	X	X	X	X	X	X	X	X
Study drug administration	<=====X=====>								
Adverse event inquiry	X	X	X	X	X	X	X	X	X
Concomitant medication inquiry	X	X	X	X	X	X	X	X	X
Plasma sample for biomarker analysis					X ^c		X	X ^c	

Abbreviations: Clinical Global Impression of Change (CGI-C); Columbia-Suicide Severity Rating Scale (C-SSRS); electrocardiogram (ECG); End of Study (EoS); Early Termination (ET); Follow-up (F/U); Huntington Disease Quality of Life Questionnaire (HDQoL); Open-label Extension (OLE); Problem Behaviors Assessment – Short Form (PBA-s); Symbol Digit Modalities Test (SDMT); Stroop Word Reading (SWR); Total Functional Capacity (TFC); Total Motor Score (TMS); Unified Huntington Disease Rating Scale (UHDRS); Visit (V); women of childbearing potential (WOCBP).

Table Footnotes:

- The OLE V1 is the same as Main Study V8 (or V7/W65 for the last participant in the Main Study). Assessments do not need to be repeated if conducted as part of the Main Study.
- A participant who discontinues study drug at any point during the OLE, must also be withdrawn from the study and attend an EoS visit.
- In-clinic visit window can be expanded to ±28 days; this applies to all in-clinic visits including OLE V1-4+ and OLE F/U. The expansion of the in-clinic visit window is only in case of a global pandemic.
- Collect blood after ECG is administered (not before).
- Urinalysis will be done as part of Main Study V8, not as part of OLE
- Triple ECG pre-dose.
- Single ECG 1-2 hours post-dose.
- Single ECG pre-dose.

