8.4. Adverse Events

All AEs will be coded using MedDRA Version 23.0 (or a later version if updated during the study).

For statistical analysis, a TEAE is defined as an AE that occurs for the first time or worsens (as captured on the eCRF) on or after initiation of treatment in the corresponding analysis period (Main Study or OLE Treatment Period) EoS. Due to the short half-life of Pridopidine (10-12 hrs) AEs that started more than 14 days after end of treatment are not considered TEAEs.

The terms AEs and TEAEs are used interchangeably in this SAP and unless otherwise specified refer to TEAEs.

An overall summary will be presented by treatment groups that includes the number and percentage of participants who experienced at least one TEAE for the following categories: All TEAEs, serious TEAEs, TEAEs leading to study discontinuation, TEAEs leading to death, TEAEs based on maximal Severity, TEAEs leading to study drug withdrawal anytime during the study, TEAEs leading to study drug withdrawal during titration. When appropriate, a total column may appear as the last column.

Summaries will be presented for all TEAEs by SOC and PT for the following categories of TEAEs:

- TEAEs, severe TEAEs, Treatment-related TEAEs, Serious TEAEs (see below for more details), TEAEs potentially related to QT prolongation, (e.g., palpitations, dizziness, syncope, cardiac arrhythmias, and sudden death), TEAEs related to abuse potential (See Appendix 12.2 for the AE terms), TEAEs causing discontinuation from the study.

The above summaries will include the number of events as well as number and percentage of participants experiencing at least one TEAE in each SOC and PT. To count the number of participants with any TEAEs, a participant who experiences multiple TEAEs within the same SOC will be counted only once for that SOC (if the TEAEs are coded to the same PT). A participant who experiences multiple TEAEs coded to the same PT within the same SOC will be counted only once for that PT. The number and percentage of participants experiencing any TEAE will also be provided. All percentages will use the number of participants in the SP within that treatment group as the denominator. In the summaries SOCs will be sorted in descending order based on number of participants in Total column; PT within SOC will be sorted by descending number of participants in Total column.

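### SAP 5.5.7 starts the OLE Treatment Period a day after the scheduled first open-label dose, so adverse events that follow that dose on the same day count as double-blind events, under placebo for former placebo participants

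*SAP*

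**What the plan says.** SAP 5.5.7 defines the two treatment periods. The Main Study Treatment Period "is defined as the period from the first dose to the End of the Main Study Day". The OLE Treatment Period "is defined as the period from 1 day after End of the Main Study Day to End of OLE Day". The End of the Main Study Day "for a participant is defined as the Main Study EoS/ET Visit, or last follow-up safety visit or phone call in the Main Study". The follow-up contact does not apply to those who continue, because Table 1, footnote c says: "Follow-up visit in Main Study is only applicable to participants who are not continuing to Open-label Extension".

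SAP 3.1 says that "eligible participants will have the option to enroll into an OLE period, commencing at the Main Study EoS visit". The OLE schedule (SAP Table 2) labels the first column "OLE Day 1 (same as Main Study Wk 78/EoS". Its ECG cell carries two footnotes: a pre-dose triplicate and a "Single ECG 1-2 hours post-dose". Protocol Table 3 is the same.

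SAP 8.4 counts an adverse event as treatment-emergent if it first occurs or worsens "on or after initiation of treatment in the corresponding analysis period (Main Study or OLE Treatment Period". SAP 6.5 attributes concomitant medications by the same two periods. SAP 4.1.5 labels a participant's double-blind treatment by the doses received in the double-blind period.

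**The concern.** The period boundary and the dosing schedule disagree by one day, and that day includes the first exposure of former placebo participants to active drug. An adverse event that begins a few hours after that exposure is dated inside the Main Study period. Since the double-blind label depends only on double-blind doses, the participant is still classed as placebo.

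The extra day exists in both arms, so background events should roughly balance. Events caused by first exposure do not balance: in former placebo participants they are added to the placebo column. For drug-caused events this can only narrow the randomised difference. The same events also fall outside the OLE period as 5.5.7 draws it.

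**Working it through.** No planned figure is involved, so the check sets the definitions side by side and then sizes the overlap.

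**Dates.** Let D be the EoS visit date of a participant who enters the OLE.

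1. End of the Main Study Day = D (5.5.7, with the follow-up contact ruled out by Table 1, footnote c).
2. OLE Day 1 = D (3.1 and Table 2).
3. First open-label dose = D, because the OLE Day 1 visit has both a pre-dose and a 1-2 hour post-dose ECG.
4. Main Study Treatment Period = [first double-blind dose, D], which contains D.
5. OLE Treatment Period = [D + 1, End of OLE Day], which does not contain D.

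The result is the same whether EoS falls at Week 65 or Week 78; Table 2, footnote a treats a Week 65 EoS as OLE V1 in the same way.

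**Adverse events.** An event starting on D after the dose lies in the period at step 4. The 8.4 exclusion of events starting more than 14 days after the end of treatment does not remove it. Under 4.1.5 a former placebo participant remains placebo for the double-blind period.

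**Medications.** Under 6.5, a drug started on D is attributed to the Main Study period. Section 6.5 lets one medication count in both periods, so a drug that continues past D also appears in the OLE. Only one taken solely on D is lost from the OLE.

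**Size.**

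- Week 65: 65 × 7 + 1 = 456 days; 1/456 = 0.22% of the Main Study period.
- Week 78: 78 × 7 + 1 = 547 days; 1/547 = 0.18%.
- Two-week OLE titration: 1/14 = 7.1% of its days.
- Placebo participants: 240 at most under the planned arm size (SAP 3.1). The SAP version history reports 499 randomised, about 250 per arm at 1:1 (499/2 = 249.5). OLE uptake is not given. Assuming 70% to 95% of 240, the count is 0.70 × 240 = 168 to 0.95 × 240 = 228 participant-days. These are days, not events.

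**ECGs.** SAP 8.8.2 presents quantitative ECG results by scheduled visit and time point and does not use the treatment periods. SAP 5.5.8 bases by-visit analyses on nominal visits. For OLE entrants the Main Study schedule has only a pre-dose triplicate at V8 (Table 1, footnote q); the post-dose ECG is only in the OLE schedule. SAP 5.5.1.2 gives the OLE its own ECG baseline from the pre-dose triplicate. SAP 8.1 splits safety data by study portion. None of this places the post-dose ECG in the Main Study. Nothing expressly excludes it either, and SAP 5.4 takes in every post-baseline value for abnormality summaries without a cut at the first OLE dose.

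**The case against.** The strongest reply is that this is an inconsistency at a boundary, not a settled misallocation. SAP 4.1.5 and 5.5.1.2 both refer to a first pridopidine dose in the OLE period, and 5.5.1.2 generally puts the OLE baseline on OLE Day 1, so parts of the SAP treat that day as OLE. The 8.4 wording about initiation of treatment in the corresponding period could be read the same way. This stands in part: loss from the OLE tables follows from the 5.5.7 boundary, but another section can be read differently. It does not undo the Main Study allocation, since 5.5.7 keeps day D in that period on either reading.

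A second reply is that the dose sequence on day D is not fully fixed. Table 1 has a PK sample at V8, drawn 1-2 hours after dosing and after the ECG, and does not say whether that dose is the last double-blind or the first open-label capsule. The OLE ECG footnotes and the OLE baseline rule favour an open-label dose that day. If it were taken on a later date, the overlap would disappear.

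A third reply is that a next-day boundary is a simple date-only convention that avoids counting a day twice, and that 5.8.2 handles adverse events by start date, with no statement that onset time is collected. This is fair, and it shapes the fix: moving the boundary to the calendar day alone would reverse the error for pre-dose events.

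A reader might also infer that the OLE Day 1 post-dose ECGs of former placebo participants enter the placebo column and distort the QTcF comparison. The documents do not support that, for the reasons given under the ECG check. The risk arises only if records are split by date, or if the 5.4 rule is applied without a cut at the first OLE dose. The randomised post-dose ECG at Baseline (V2) is unaffected.

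**Conclusion.** The point holds for adverse events and newly started medications. As written, 5.5.7 assigns those that follow the scheduled first open-label dose on the EoS day to the double-blind period, and to placebo for former placebo participants. The conclusion assumes that dosing takes place on OLE Day 1 as scheduled.

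The effect is minor: one day per OLE entrant and a slight dilution of the randomised adverse-event comparison toward no difference. Participants on pridopidine in both periods keep the right drug label although the period is wrong. For the OLE Day 1 post-dose ECG, the finding is an unstated rule and a risk, not a demonstrated misallocation.

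**What to change.** Amend SAP 5.5.7 so that the Main Study Treatment Period ends immediately before the first OLE dose and the OLE Treatment Period begins with it, using date and time where both are available. Add a default: an event dated that day without an onset time goes to the OLE unless it is recorded as starting before the dose. Apply the same boundary to concomitant medications in 6.5. State in 8.8.2 that the OLE Day 1 post-dose ECG belongs to the OLE and is excluded from Main Study abnormality summaries.

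The cost is a few sentences of SAP text and the matching programming. The default has a small downside: some pre-dose events on that day will move to the OLE. SAP section 5 gives the route: an addendum if made before database lock and unblinding, otherwise a description in the clinical study report as a change to the planned analyses.
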